9.2.2 Adverse Event Overview

An overview of AEs will be presented consisting of the number and percentage of subjects experiencing at least one event for each of the following AE categories:

- Any treatment-emergent AE
- Any treatment-emergent AE related to COVID-19
- Any treatment-emergent AE related to study drug according to the investigator
- Any severe treatment-emergent AE
- Any serious treatment-emergent AE
- Any treatment-emergent AE leading to discontinuation of study drug
- Any treatment-emergent AE leading to death
- Treatment-emergent AEs of Safety Interest including
 - Adjudicated MACE events
 - Serious infections
 - Active Tuberculosis
 - Opportunistic infections excluding tuberculosis and herpes zoster
 - Malignant tumors
 - Malignancies excluding NMSC
 - Hypersensitivity – serious events only
 - Adjudicated anaphylactic reaction
 - Serious anaphylactic reaction
- All deaths
 - Deaths occurring \leq 140 days after last dose of study drug
 - Deaths occurring $>$ 140 days after last dose of study drug
 - Deaths related to COVID-19

The exposure adjusted rate for AE overview will be presented as well.

9.2.3 Treatment-Emergent Adverse Events by SOC and/or PT

Treatment-emergent adverse events will be summarized by SOC and PT; by maximum relationship to study drug as assessed by the investigator (e.g., reasonable possibility or no reasonable possibility) and SOC and PT; by maximum severity and SOC and PT; and by subject number and SOC and PT. Specific adverse events will be counted once for each subject for calculating percentages, unless stated otherwise. In addition, if the same adverse event occurs multiple times within a subject, the highest severity and level of relationship to investigational product will be reported.

In addition, treatment-emergent adverse events and SAEs will be summarized by PT and sorted by decreasing frequency for the total risankizumab group.

9.2.4 Treatment-Emergent Adverse Events per Patient-Years of Exposure

Exposure-adjusted AEs per 100 patient-years will be provided for all TEAEs, where AEs per 100 patient-years of exposure are defined as the number of AEs divided by the total exposure in 100 patient-years, where the total exposure is calculated as the time from the first study drug dose date in the relevant period/study to the last study drug dose date +140 days in the relevant period/study or the first dose date of the next period/study, whichever occurs earlier.

The exposure adjusted incidence rate (censored at the time of first event) may be conducted for deaths and selected Areas of Safety Interest categories including adjudicated cardiovascular events, malignant tumors, non-melanoma skin cancer (NMSC), and malignant tumors excluding NMSC, as appropriate.

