2.2 Study Design Overview

This is a Phase 3, multicenter, randomized, double-blind, placebo-controlled study designed to evaluate the efficacy and safety of risankizumab as an induction therapy in subjects with moderately to severely active CD.

The study consists of the following periods:

1. Screening period of up to a maximum of 35 days
2. 12-week randomized, double-blinded IV therapy induction period (12-Week Induction Period)
3. 12-week randomized, double-blinded, double-dummy Induction Period 2 (Induction Period 2) for subjects who do not achieve clinical response at Week 12
4. 20-week follow up period from the last dose of study drug.

The schematic of the study is shown in [Figure 1](#).

Figure 1. Study Schematic

[figure not shown]
[figure not shown]

Figure 1. Study Schematic (Continued)

DC = discontinued; IR = subjects with inadequate clinical response to induction; IV = intravenous; R = subjects with clinical response; RR = re-randomize

Approximately 855 patients with moderate to severe CD who had baseline eligible SES-CD (eligible SES-CD is defined as total SES-CD score excluding presence of narrowing subscore) of ≥ 6 (≥ 4 for isolated ileal disease) are to be randomized in a ratio of 2:2:1 to one of the three following treatment groups in the 12-Week Induction Period.

- Placebo IV (n = 342)
- Risankizumab 600 mg IV (n = 342)
- Risankizumab 1200 mg IV (n = 171)

In addition to the 855 subjects, up to 85 subjects with a lower SES-CD, defined as an eligible SES-CD of ≥ 3 to < 6 for ileocolonic or colonic disease or SES-CD of 3 for isolated ileal disease will be enrolled in order to inform treatment effect in this patient population, but these subjects will not be included in the primary ITT population for efficacy analysis.

Each treatment group receives the corresponding dose of risankizumab or placebo IV infusion at Week 0, Week 4, and Week 8. At Week 12, patients are evaluated for clinical response, defined as $\geq 30\%$ decrease in average daily SF and/or $\geq 30\%$ decrease in average daily AP score and both not worse than baseline.

Visits for clinical evaluation will occur at baseline/Week 0, Weeks 4, 8, and 12 or Premature Discontinuation (PD).

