5.0 Subject Disposition

The total number of subjects who were enrolled, randomized and treated will be summarized.

A summary of subject accountability will be provided where the number of subjects in each of the following categories will be summarized for each treatment group:

- Subjects enrolled/randomized in the study
- Subjects who took at least one dose of study drug (ITT1A for the 12-Week Induction Period, ITT2 for the Induction Period 2 and ITT1 for the entire study)
- Subjects who completed study drug (SA1A for the 12-Week Induction Period, SA2 for the Induction Period 2 and SA1 for the entire study)
- Subjects who prematurely discontinued study drug (SA1A for the 12-Week Induction Period, SA2 for the Induction Period 2 and SA1 for the entire study)
- Subjects who prematurely discontinued from study (ITT1A for the 12-Week Induction Period, ITT2 for the Induction Period 2 and ITT1 for the entire study)
- Subjects who completed study (ITT1A for the 12-Week Induction Period, ITT2 for the Induction Period 2 and ITT1 for the entire study)

For end of study participation, the number and percentage of subjects who completed the protocol defined follow-up period (or did not with associated reasons) will be summarized overall and by treatment group.

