8.0 Efficacy Analyses

8.1 General Considerations

The primary and secondary efficacy endpoints as specified in Section 3.1 and Section 3.2 will be analyzed based on ITT1A for 12-Week Induction Period. The difference between

treatment groups for the primary and ranked secondary efficacy endpoints will be tested with graphical multiplicity adjustment¹ to ensure a strong control of family-wise type I error rate at significance level $\alpha = 0.05$ (two-sided) (see Section 11.0). Analyses of other efficacy endpoints for 12-Week Induction Period as specified in Section 3.3 will be performed using ITT1A at the nominal significance level $\alpha = 0.05$ (two-sided) without multiplicity adjustment.

Analyses for other efficacy endpoints as specified in Section 3.3 for Induction Period 2 will be performed using ITT2A. Since the Induction Period 2 is for exploratory purpose, no multiplicity adjustment will be performed.

For all efficacy endpoints, the descriptive statistics will be provided by period and by treatment group in which the subjects were randomized to at the beginning of each period. The statistics include number of observations, mean, standard deviation, minimum, median, and maximum for continuous variables, and number and percent for discrete variables.

Unless otherwise specified, any subject who is randomized based on a wrong stratum will be analyzed according to the actual stratum the subject belongs to.

When all subjects complete their Week 12/PD visit, the database will be locked and un-blinded for the 12-Week Induction Period. The planned analysis for the 12-Week Induction Period will be performed. This is the only and final efficacy analysis for the 12-Week Induction Period. When all the subjects who enter the Induction Period 2 finish Week 24/PD visit, the database will be locked for the whole study and all the planned analysis for the Induction Period 2 will be performed.

Analysis of Binary Variables:

For binary variables, frequencies and percentages will be reported for each treatment group. Pairwise comparison of each risankizumab group and placebo will be performed using the Cochran Mantel-Haenszel (CMH) test adjusting for stratification factors. If there is a stratum for a treatment group that has no subject in it, a value of 0.1 will be

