9.0 Safety Analyses

9.1 General Considerations

Safety analyses will include reporting of adverse events, laboratory, and vital signs measurements by treatment group, including a total group for all subjects on

risankizumab. All safety analyses will be performed for the 12-Week Induction Period at the time of database lock. The separate safety analysis for subjects who received at least one dose of risankizumab during the Induction Period 2 will be performed.

The following summary statistics will be presented for subjects who have both baseline and post-baseline values for laboratory parameters and vital signs: the mean value at baseline and at each respective protocol specified visit, and the mean, standard deviation and median for changes from baseline. Categorical data will be summarized using frequencies and percentages. The risk difference and 95% CI between each risankizumab group and placebo group will be presented for safety analysis.

For the safety analysis, subjects are assigned to a treatment group based on the treatment actually received, regardless of the treatment randomized.

For the 12-Week Induction Period analysis, the baseline for safety analysis is defined as the last available measurement before study drug administration for all subjects. For the Induction Period 2 analysis, the baseline for safety analysis will be the last available measurement before the first dose of risankizumab administration in Induction Period 2.

Missing safety data will not be imputed.

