9.2.1 Treatment-Emergent Adverse Events

12-Week Induction Period: Treatment emergent AEs (TEAEs) for the 12-Week Induction Period are defined as events that begin either on or after the first dose of the study drug in the 12-Week Induction Period and until the first dose of study drug in the Study M16-000 if the subject is enrolled into the Study M16-000 or until first dose of study drug in Induction Period 2 if the subject is enrolled into Induction Period 2, or within 140 days after the last dose administration of the study drug in 12-Week Induction Period if the subject does not participate in the Study M16-000 or the Induction Period 2.

Induction Period 2: Treatment-emergent AEs (TEAEs) for the Induction Period 2 are defined as events that begin either on or after the first dose of the study medication in the Induction Period 2 and until first dose of study drug in the Study M16-000 if the subject is enrolled into the Study M16-000 or within 140 days after the last dose of the study drug in the Induction Period 2 if the subject does not participate in the Study M16-000.

All Risankizumab: Treatment-emergent AEs (TEAEs) for "All Risankizumab" are defined as events that begin either on or after the first dose of risankizumab and until first dose of study drug in the Study M16-000 if the subject is enrolled into the Study M16-000 or within 140 days after the last dose of risankizumab in the study if the subject does not participate in the Study M16-000.

Events where the onset date is the same as the study drug start date are assumed to be treatment-emergent, unless the study drug start time and the adverse event start time are collected and the adverse event start time is prior to the study drug start time. If an incomplete onset date was collected for an adverse event, the event will be assumed to be treatment-emergent unless there is other evidence that confirms that the event was not treatment-emergent (e.g., the event end date was prior to the study drug start date).

All treatment-emergent AEs will be summarized overall, as well as by primary MedDRA SOC and Preferred Term. The SOCs will be presented in alphabetical order, and the PTs will be presented in alphabetical order within each SOC.

The number and percentage of subjects experiencing treatment-emergent AEs will be summarized. The risk difference and 95% CI between each risankizumab group and placebo group will be presented.

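### Exposure-adjusted AE rates have no stop at death, last contact or data cut-off, so subjects with curtailed follow-up add unobserved time and the rates can only be biased low

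*SAP*

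**What the plan says.** Section 9.2.4 defines the rate: "AEs per 100 patient-years of exposure are defined as the number of AEs divided by the total exposure in 100 patient-years". Time runs from the first dose in the period or study "to the last study drug dose date +140 days in the relevant period/study or the first dose date of the next period/study", whichever is earlier. Those are the only two end points named. The section adds an optional incidence rate, censored at first event, for deaths and selected safety-interest categories.

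Exposure-adjusted figures are also planned for the AE overview (Section 9.2.2), SAEs (9.2.5) and areas of safety interest (9.2.6). Section 9.2.4 holds the only definition of the denominator.

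The 140 days agree with two other places. Section 2.2 plans a "20-week follow up period from the last dose of study drug", and Section 9.2.1 counts an AE of the first period as treatment-emergent if it begins "within 140 days after the last dose administration of the study drug in 12-Week Induction Period if the subject does not participate" in M16-000 or Induction Period 2.

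On timing, Section 8.1 states: "When all subjects complete their Week 12/PD visit, the database will be locked and un-blinded for the 12-Week Induction Period". Section 9.1 states: "All safety analyses will be performed for the 12-Week Induction Period at the time of database lock". Section 8.1 sets the whole-study lock when the last Induction Period 2 subject has the Week 24/PD visit.

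**The concern.** A person-time denominator should hold only time in which an event could have been counted. The SAP foresees several cases in which that time ends before day 140:

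- Section 9.2.2 tabulates deaths up to 140 days after the last dose.
- Section 5.0 summarises how many subjects did not complete follow-up, with reasons.
- Neither lock in Section 8.1 waits for the 140-day follow-up.
- Under Section 2.2, subjects without response at Week 24 and early terminators are called 140 days after the last dose. For some of them the call falls after the relevant lock.

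The matching TEAE window does not repair this. An event after death, loss or lock cannot reach the numerator, but the days after that point still enter the denominator. At stake are the rates per 100 patient-years for all TEAEs, SAEs and safety-interest events, which would look more favourable than the data observed.

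**Working it through.** The SAP states no exposure total, AE rate or discontinuation rate, so there is no planned figure to reproduce. The windows agree on paper: 20 weeks × 7 = 140 days.

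**Per subject.** Let L be the day of the last dose and t the days actually followed after it. Credited time is L + 140, observed time is L + t, and the excess is 140 − t. This lies between 0 and 140 and is never negative. Dosing at Weeks 0, 4 and 8 (Section 2.2) gives L = 0, 28 or 56. With t = 28:

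| Doses received | Credited days | Observed days | Excess |
|---|---|---|---|
| 1 | 140 | 28 | 112 |
| 2 | 168 | 56 | 112 |
| 3 | 196 | 84 | 112 |

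The value t = 28 also arises from the design. A Week 24 non-responder last dosed at Week 20, whose Week 24 visit coincides with the whole-study lock, has 28 days observed and 140 credited.

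**Per arm.** Let d be the share of subjects who do not continue and u the share of those whose follow-up is truncated. Both are assumptions. Further assumptions: continuing subjects contribute 84 days; non-continuing subjects had two doses (L = 28); truncated ones have t = 28.

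- Credited mean = (1 − d) × 84 + d × 168
- Observed mean = (1 − d) × 84 + d × [(1 − u) × 168 + u × 56]
- Reported rate ÷ observed-time rate = observed mean ÷ credited mean

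| d | u | Credited | Observed | Reported ÷ observed-time rate |
|---|---|---|---|---|
| 5% | 25% | 88.2 | 86.8 | 98.4% |
| 5% | 100% | 88.2 | 82.6 | 93.7% |
| 10% | 25% | 92.4 | 89.6 | 97.0% |
| 20% | 25% | 100.8 | 95.2 | 94.4% |
| 20% | 100% | 100.8 | 78.4 | 77.8% |

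Over a wider grid (d from 2% to 30%, u from 10% to 100%) the ratio runs from 99.7% to 69.2%.

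**Between arms.** The factor on the risankizumab:placebo rate ratio is the risankizumab ratio divided by the placebo ratio.

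- Both arms d = 10%, u = 25%: 0.970 ÷ 0.970 = 1.00.
- Placebo d = 20%, risankizumab d = 5%, u = 25% in both: 0.984 ÷ 0.944 = 1.04.
- The same split with u = 100%: 0.937 ÷ 0.778 = 1.20.

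**The case against.** The best defence is that the rule fits the design. Follow-up, TEAE window and exposure all use 140 days, and non-continuing subjects get a call at day 140 to collect AEs. A subject followed that far is credited correctly. Subjects who enter M16-000 or Induction Period 2 stop at the next first dose. The planned between-arm safety contrasts are risk differences presented with subject counts and percentages, which do not use this denominator, and no rate ratio or rate difference is specified. All of this stands. It limits how many subjects are affected and how much rests on the rates. It does not supply a stop for subjects who die, are lost, or are still inside the window at a lock.

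The optional incidence rate helps only in part. It ends a subject's time at the first event, so death ends time in the death rate. But it may or may not be produced, it covers few categories, and it names no other end for subjects without an event.

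Two stronger readings are tempting. A reader might infer that every non-continuing subject is over-credited. The documents do not support this: only curtailed follow-up creates excess, and a lock matters only for those last dosed within the 140 days before it. A reader might also infer that rates are understated unequally by arm, so that the comparison with placebo is distorted. The SAP gives no discontinuation, death or follow-up figures by arm, and with similar truncation and exposure the bias cancels in a ratio.

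**Conclusion.** The point holds as a defect in a stated rule. Followed exactly, Section 9.2.4 credits time after death, loss to follow-up or data cut-off, and the error has one direction: the rates are too low.

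Under the two-dose, 28-day assumptions the reported rate is about 98% of the observed-time rate when 5% do not continue and a quarter of them are truncated. It is about 78% when 20% do not continue and all are truncated. The second figure is an upper case, since it supposes that no non-continuing subject is followed to day 140.

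A difference between arms is possible, not shown. If 20% on placebo and 5% on risankizumab did not continue, the rate ratio would be multiplied by 1.04 to 1.20, which would make risankizumab look worse. The opposite imbalance would flatter it.

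The effect is confined to descriptive safety rates. Subject percentages, risk differences, efficacy results and type I error control do not change. The correction should still be made before the rates are reported.

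**What to change.** In Section 9.2.4, define the end of exposure as the earliest of: last study drug dose + 140 days, first dose of the next period or study, death, last contact or withdrawal from study, and the data cut-off date of the analysis concerned. Use this end date for every exposure-adjusted figure in Sections 9.2.2, 9.2.4, 9.2.5 and 9.2.6.

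The cost is one sentence and one change to the derivation. Reported rates become slightly higher.

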9.2.5 SAEs (Including Deaths) and Adverse Events Leading to Study Drug Discontinuation

SAEs (including deaths) and AEs leading to study drug discontinuation will be summarized by SOC and PT and in listing format. Exposure-adjusted SAEs per 100 patient-years by SOC and PT will be provided as well.

9.2.6 Areas of Safety Interest

The Areas of Safety Interest (ASI) categories are listed in [Appendix B](#), which include serious infections, tuberculosis, opportunistic infections, herpes zoster, malignancies, hypersensitivity reaction, anaphylactic reactions, hepatic events, injection site reactions, adjudicated cardiovascular events. These will be summarized by PT and will be based on standardized or company MedDRA queries (SMQs or CMQs), or based on adjudication results. The risk difference and 95% CI between each risankizumab group and placebo group will be presented. Exposure-adjusted ASI per 100 patient-years by PT or adjudication terms will be provided as well.

Additional ASI may be considered for tabulation/summary based on recommendations from Clinical and Safety teams, as deemed appropriate.

9.3 Analysis of Laboratory Data

Data collected from central and local laboratories, including additional laboratory testing due to an SAE, will be used in all analyses, except for baseline where SAE-related laboratory assessments on or before the first dose of study drug will be excluded. The clinical laboratory tests defined in the protocol (e.g., hematology and clinical chemistry) will be summarized.

Each laboratory variable will be summarized for all time points (starting with baseline) with the number of non-missing observations, mean and standard deviation, median, minimum and maximum. Mean change from baseline to each applicable post-baseline visit will be summarized for selected laboratory variables, with the number of

observations, baseline mean, and visit mean. The change from baseline mean, standard error, and 95% CI will be presented for the mean change from baseline within each treatment group and difference between each risankizumab group and placebo group.

Changes in laboratory parameters will be tabulated using shift tables either based on NCI CTC criteria or categorized as low, normal, or high based on the normal ranges of the laboratory used for each sample. A shift table from baseline either to the worse value (based on NCI CTC criteria) during treatment or to minimum and maximum value (based on normal range), will be created. A similar shift table will be provided to summarize shifts from baseline to the final post-baseline value.

Laboratory abnormalities will be evaluated based on Potentially Clinically Significant (PCS) criteria ([Appendix C](#)). For each laboratory PCS criterion, the number and percentage of subjects who have a laboratory value meeting the criteria will be summarized by treatment group. Listings will be provided to summarize subject-level laboratory data for subjects meeting PCS criteria.

The liver-specific laboratory tests include the serum glutamic pyruvic transaminase (SGPT/ALT), serum glutamic-oxaloacetic transaminase (SGOT/AST), alkaline phosphatase (ALP), and total bilirubin (TBL). The frequencies and percentages of subjects with post baseline liver specific function test values that meet the following criteria of potential clinical interest will be summarized by treatment group:

- $ALT \geq 3 \times ULN$
- $ALT \geq 5 \times ULN$
- $ALT \geq 10 \times ULN$
- $ALT \geq 20 \times ULN$
- $AST \geq 3 \times ULN$
- $AST \geq 5 \times ULN$
- $AST \geq 10 \times ULN$
- $AST \geq 20 \times ULN$
- $TBL \geq 2 \times ULN$

- Alkaline phosphatase $\geq 1.5 \times \text{ULN}$
- (ALT and/or AST $\geq 3 \times \text{ULN}$) and (TBL $\geq 1.5 \times \text{ULN}$)
- (ALT and/or AST $\geq 3 \times \text{ULN}$) and (TBL $\geq 2 \times \text{ULN}$)

where ULN is the upper limit of normal.

A listing of potentially clinically significant liver function laboratory values will be provided. The listing will include all subjects who met any of the following 4 criteria at any post-baseline visit:

- ALT $\geq 3 \times \text{ULN}$, or
- AST $\geq 3 \times \text{ULN}$, or
- Alkaline phosphatase $\geq 1.5 \times \text{ULN}$, or
- Total bilirubin $\geq 1.5 \times \text{ULN}$.

A listing of possible Hy's Law cases, defined as those who meet all of the following conditions at any post-baseline visit will be provided:

- ALT of $> 3 \times \text{ULN}$ or AST of $> 3 \times \text{ULN}$,
- Total bilirubin $\geq 2 \times \text{ULN}$.

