2.4 Sample Size Determination

For US-specific protocol, the co-primary endpoints are the achievement of CDAI clinical remission at Week 12 and the achievement of endoscopic response at Week 12. For global protocol outside US, the co-primary endpoints are the achievement of clinical remission at Week 12 and the achievement of endoscopic response at Week 12.

Sample size calculation is based on the larger sample size needed to detect treatment difference between the risankizumab treatment group and the placebo group for each of the co-primary endpoints. Since historical data show slightly lower event rate and similar treatment difference for the endoscopic response rate compared to the clinical remission rate at Week 12, as well as the larger treatment difference for the CDAI clinical remission rate compared to the clinical remission rate at Week 12, clinical remission rates at Week

12 are used for power calculation. A total of 855 subjects will be randomized into the two risankizumab treatment groups and the placebo group in a 2:2:1 ratio (342 subjects for the risankizumab 600 mg dose group, 342 subjects for the risankizumab 1200 mg dose group, and 171 subjects for the placebo group). Assuming the clinical remission rate at Week 12 will be 27.8% for one of the risankizumab treatment groups and 12% for the placebo group, a sample size of 342 subjects for the risankizumab group and 171 for the placebo group will have 97% power to detect the treatment difference between risankizumab and placebo using a Fisher's exact test at a 0.025 significant level (two-sided). Assuming the Week 12 CDAI clinical remission rate will be 37% for one of the risankizumab treatment groups and 17% for the placebo group, this sample size will have 99% power to detect the treatment difference between risankizumab and placebo using a Fisher's exact test at a 0.025 significant level (two-sided). Assuming the Week 12 endoscopic response rate will be 25.5% for one of the risankizumab treatment groups and 8% for the placebo group, this sample size will have 99% power to detect the treatment difference between risankizumab and placebo using a Fisher's exact test at a 0.025 significant level (two-sided).

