8.3.2 Continuous Endpoints

For continuous efficacy endpoints where Mixed-Effect Model Repeat Measurement (MMRM) analysis or Analysis of Covariance (ANCOVA) is performed, missing data will be handled using the following approaches.

- **Mixed-Effect Model Repeat Measurement (MMRM):** The repeat measurement analysis will be conducted using a mixed model including observed measurements at all post-baseline visits, after the CD-related corticosteroids censoring rule is applied (see Section 8.2.2 and Appendix J). The mixed model includes the categorical fixed effects of treatment, visit and treatment-by-visit interaction, stratification factors at randomization, and the continuous fixed covariates of baseline measurement. An unstructured variance covariance matrix will be used. Parameter estimation is based on the method of restrictive maximum likelihood (REML). MMRM will be the primary approach in the analysis of continuous variables.
- **ANCOVA-C:** For continuous efficacy variables that are collected at only one post-baseline visit (such as SES-CD), the missing data due to COVID-19 will be imputed using MI first before applying the ANCOVA model.

In addition, As Observed (AO) and Pattern Mixture Model (PMM) will be performed as sensitivity analysis, if appropriate, for categorical or continuous endpoints.

- **As Observed (AO):** The AO analysis will not impute values for missing evaluations, and thus a subject who does not have an evaluation on a scheduled visit will be excluded from the AO analysis for that visit. AO will include all values collected in the study regardless of censoring for steroids or not.

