9.4 Analysis of Vital Signs

Vital sign measurements of systolic and diastolic blood pressure, pulse rate and body weight will be summarized.

Each vital sign variable will be summarized for all time points (starting with baseline) with the number of non-missing observations, mean and standard deviation, median, minimum and maximum. Mean change from baseline to each applicable post-baseline visit will be summarized for each vital sign variable, with the number of observations, baseline mean, and visit mean. The change from baseline mean, standard error, and 95%

CI will be presented for the mean change from baseline within each treatment group and difference between each risankizumab group and placebo group.

Key vital sign variables will be evaluated based on potentially clinically significant (PCS) criteria ([Appendix C](#)). For each vital sign PCS criterion, the number and percentage of subjects who have a vital sign value meeting the criteria will be summarized. Listings will be provided to summarize subject-level vital sign data for subjects meeting PCS criteria.

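### Laboratory and vital-sign differences from placebo have no stated baseline adjustment; adding baseline as a covariate would narrow their 95% CIs modestly at almost no cost

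*SAP*

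**What the plan says.** SAP Section 9.3, on selected laboratory variables: "The change from baseline mean, standard error, and 95% CI will be presented for the mean change from baseline within each treatment group and difference". The difference meant is that of either risankizumab dose from placebo. SAP Section 9.4 repeats this, at the same 95% level, for blood pressure, pulse and weight: "CI will be presented for the mean change from baseline within each treatment group and difference between each risankizumab group and placebo group".

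Neither section says how the between-group interval is to be obtained. No model, covariate or CI formula is given. SAP Section 9.1 sets the frame: the continuous safety summaries include "the mean, standard deviation and median for changes from baseline", in subjects measured both at baseline and afterwards, and "Missing safety data will not be imputed".

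Baseline adjustment is written out only for continuous efficacy endpoints. SAP Section 8.3.2 puts "the continuous fixed covariates of baseline measurement" into the mixed model, and Section 8.5.1 repeats this for the continuous secondary endpoints.

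**The concern.** The plan promises a comparative estimate with an interval but is silent on method. Elsewhere it names baseline as a covariate when it wants one. The safety difference is therefore likely to be programmed as one mean change minus another.

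A simple difference in change scores fixes the slope of follow-up on baseline at 1. When the true slope is below 1, this has two consequences:

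- The interval is wider than it need be.
- A chance difference between the groups at baseline leaks into the estimated difference in change through regression to the mean.

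What is at stake is some precision in the continuous-scale comparison of laboratory values and vital signs with placebo. The variable needed to recover it is already in hand for every subject summarised.

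**Working it through.** **The plan's own figures.** The SAP gives no expected width, SD or correlation for these intervals, so there is no stated figure to reproduce for them. Group sizes come from SAP Section 2.4: "a sample size of 342 subjects for the risankizumab group and 171 for the placebo group will have 97% power". As a check on those sizes, the power was recomputed with the rates given there (27.8% and 12%, two-sided 0.025). Fisher's exact test gives 97.7% and the normal approximation 97.9%, which agrees with the stated 97%. The arm list in Section 2.2 attaches 342 to placebo and 171 to the 1200 mg dose, unlike Section 2.4. The width ratio below does not depend on group sizes.

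**Assumptions.** The variance SD² is the same at baseline and follow-up. The within-group correlation is rho, shown as a range because the SAP gives none.

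**Formulas.**

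- Variance of the raw difference in change: 2(1 - rho) × SD² × (1/n1 + 1/n2)
- Variance of the ANCOVA difference: (1 - rho²) × SD² × (1/n1 + 1/n2)
- Ratio of CI widths: sqrt(2(1 - rho)/(1 - rho²)) = sqrt(2/(1 + rho))
- Shift in the raw difference caused by a baseline imbalance d: (rho - 1) × d

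**Numbers.** sqrt(1/342 + 1/171) = 0.0937, and 1.96 times the unrounded value is 0.1836. Half-widths and shifts are in SD units.

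| rho | Raw half-width | ANCOVA half-width | Ratio | Shift for a 0.1 SD imbalance |
|---|---|---|---|---|
| 0.5 | 0.184 | 0.159 | 1.15 | -0.05 |
| 0.7 | 0.142 | 0.131 | 1.08 | -0.03 |
| 0.8 | 0.116 | 0.110 | 1.05 | -0.02 |
| 0.9 | 0.082 | 0.080 | 1.03 | -0.01 |

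An imbalance of 0.1 SD is about one standard error (0.094 SD), so it is an ordinary event. At the low end, rho 0.3 gives 0.217 against 0.175, or 24% wider.

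**In units.** Take hemoglobin with an assumed SD of 1.5 g/dL and rho 0.7. The raw half-width is 1.5 × 0.1422 = 0.213 g/dL, and the adjusted one is 1.5 × 0.1311 = 0.197 g/dL. A baseline imbalance of 0.2 g/dL, about 1.4 standard errors (0.2/0.14), moves the raw difference by (0.7 - 1) × 0.2 = -0.06 g/dL.

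**Simulation.** With 1,500 simulated trials of 342 against 171 at each rho, the width ratios were 1.154, 1.083 and 1.025 at rho 0.5, 0.7 and 0.9. The slope of the raw difference on the baseline imbalance was -0.53, -0.30 and -0.10. For ANCOVA it lay between -0.02 and 0.00.

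**Without equal variances.** The variance of the raw change equals the ANCOVA residual variance plus (slope - 1)² times the baseline variance. In samples of this size, adjustment therefore costs essentially nothing, and the gain vanishes only when the slope is 1.

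**The case against.** The strongest reply is that nothing here is wrong. Under randomization, a difference in mean change is unbiased and its 95% CI has the right coverage. Chance baseline imbalance is part of the sampling error which that CI already reflects. Section 9 is descriptive, plans no p-value for these differences and lies outside the type I error plan. Baseline means are tabulated beside the visit means, so a reader can see an imbalance. All of this stands, and it limits the point to precision.

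A reader might infer more than the SAP supports in four ways:

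- **That the plan prescribes raw differences.** It never says so. It leaves the method open, and unadjusted is only the natural reading of that silence.
- **That regression to the mean makes the estimate biased.** It does so only conditionally on the imbalance that happens to occur, not over randomization.
- **That these are the only comparisons with placebo for laboratory and blood-pressure data.** Section 9.1 provides in general terms for risk differences with 95% CIs in the safety analysis, and Sections 9.3 and 9.4 tabulate threshold abnormalities by group. These differences are the comparison on the continuous scale.
- **That the efficacy models make the safety summaries inconsistent.** The efficacy models serve alpha-controlled tests, and the safety summaries do not.

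Two practical objections also have some force. A linear baseline slope may suit skewed variables, such as liver enzymes, poorly. An adjusted difference will also not equal the difference of the raw within-group means printed beside it. The first is met by a log scale for such variables, and the second by a footnote.

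**Conclusion.** The point holds as a minor improvement. Sections 9.3 and 9.4 promise a difference from placebo with a 95% CI and state no baseline adjustment, although the baseline value is available for every subject summarised. If computed without adjustment, the CI is valid but about 3% (rho 0.9) to 15% (rho 0.5) wider than with baseline as a covariate. Since the share of subjects is (1 - rho)/2, that is equivalent to discarding about 5% to 25% of them. A chance imbalance carries over by (rho - 1) times its size.

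These figures rest on an assumed rho and on equal variances at baseline and follow-up. The gain will differ between variables and will be close to nil for those that track their baseline closely. No conclusion of the trial depends on it.

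**What to change.** In Sections 9.3 and 9.4, state that each difference from placebo and its 95% CI, at each visit, comes from an ANCOVA of the change from baseline with treatment group and baseline value as terms. For laboratory variables that are markedly skewed, use the log scale and name those variables before unblinding. Keep the within-group means, standard errors and CIs as they are. Add a table footnote saying that the difference is baseline-adjusted and need not equal the difference of the displayed means (and is a ratio where the log scale is used).

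The cost is a sentence or two of SAP text and one model statement per parameter and visit. It needs no new data, uses the same subjects and leaves the type I error plan untouched.
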